In our study in pregnant patients, 1 gram intravenous TXA (or placebo) will be administered immediately after delivery of the infant and after clamping of the umbilical cord to avoid any potential fetal effects. The drug will be prepared and ready to hang at the beginning of the case.

Drug preparation will include the following: Removal of 20 ml from a 50 ml bag of D5W and injection of 10 milliliters of 100mg/ml TXA resulting in a final total volume of 40 ml. Placebo will be prepared by removing 10 ml from a 50 ml bag of D5W. The final volume of the study drug and the placebo bags will be the same and identical in appearance.

Anesthesia staff (physicians and nurse anesthetists) working in the trauma operating rooms will have an in-service about the research study and procedures at a weekly staff meeting to ensure proper education and compliance with study protocol. Intravenous TXA or placebo will be given to the randomized patients by CRMC anesthesia staff after the cord has been clamped and cut based on the intraoperative findings.

All patients undergoing cesarean at high risk for accreta at CRMC have two large bore IVs placed preoperatively. The patient will not require an additional IV for the study drug. TXA is delivered in 5% dextrose plain water and this can be hung as a piggyback with the patient's intraoperative fluids. TXA is clear and colorless and will be visually indistinguishable from the placebo. The hospital pharmacy will be able to provide the placebo.

Primary outcome: The primary endpoint will be estimated intraoperative blood loss (EBL), which is routinely recorded at the end of all operative cases. EBL is *estimated* by the operating room team following a discussion between the surgeon and anesthesia staff based on number of tapes / sponges used, amount of fluid in suction canister, amount of blood on the floor, etc. Secondary endpoints will include amount of blood transfusion, preop and post operative hemoglobin levels, length of hospital stay, ICU admission rates and length of stay, and post-operative complications (DVT, PE, surgical site infection). Maternal demographic information, medical comorbidities, and infant outcomes (weight, Apgar scores, NICU admission) will also be recorded with chart review.

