All UCSF generalists (including [name]) and residents (co-investigators) will be involved in the post operative care of these patients. There is an "attending of the day" for Labor & Delivery who rounds on high risk post partum patients with the residents and directly supervises resident care of these patients. A resident co-investigator will closely follow the patient throughout their post-operative course. Standard clinical care involves a "PM check" (evening visit to see the patient on the day of surgery), as well as daily morning rounding by a resident and attending faculty. *The principle investigator [name] will be notified of all potential adverse events by frequent communication with the resident team and with chart review, starting on post operative day zero, and continuing daily throughout the length of the patient's hospitalization.*

Patients will be called by the PI or a co-investigator 24-48 hours after discharge to evaluate for any clinical needs at home and to monitor for potential adverse events. Patients will be seen at 2 and 6 weeks post operatively in clinic (if their health insurance allows this) by a resident co-investigator and UCSF faculty which is standard for post partum / post surgical care. If a patient no-shows to a post partum visit, they will be called to ask them to reschedule, and a letter will be sent to the home address to improve follow up rates.

Patients will not be followed beyond the 6 week post partum visit. A copy of the consent form, including the drug risks, will be provided to each patient in the study to be given to their primary care doctor for future care.

If a significant adverse event occurs at any point during the study, the research pharmacy technician will be notified and that patient will be unblinded to the lead study investigator. The principle investigator will present the patient and adverse events to the safety monitoring committee for discussion and potential action in a timely fashion (within 48 hours for significant adverse events (blood clot, patient death) and within one week for minor adverse events (rash, nausea/vomiting).

Risks to Human Subjects

The proposed research activities qualify as Human Subjects Research and meet the definition of clinical research, as described fully below.

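### Clinic follow-up at 2 and 6 weeks depends on insurance, so some women may have no planned study contact after the 24-48 hour call and late DVT, PE or infection may be under-counted

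*Combined protocol and SAP*

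**What the plan says.** The Primary outcome paragraph lists among the secondary endpoints "post-operative complications (DVT, PE, surgical site infection", with no time window. Potential Risks names thrombosis as the theoretical hazard of TXA and describes pregnancy and the post partum period as hypercoagulable.

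Adverse Events Monitoring sets out how such events would come to light:

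- **In hospital.** The investigator learns of possible events from the resident team and "with chart review, starting on post operative day zero, and continuing daily throughout the length of the patient's hospitalization".
- **Just after discharge.** "Patients will be called by the PI or a co-investigator 24-48 hours after discharge".
- **Later.** "Patients will be seen at 2 and 6 weeks post operatively in clinic (if their health insurance allows this".
- **Missed visits.** "If a patient no-shows to a post partum visit, they will be called to ask them to reschedule, and a letter will be sent".
- **End of follow-up.** "Patients will not be followed beyond the 6 week post partum visit".

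Two other statements bear on the point. The same section says "A resident co-investigator will closely follow the patient throughout their post-operative course". The Primary outcome paragraph says that demographics, comorbidities and infant outcomes "will also be recorded with chart review".

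**The concern.** The last contact planned for every woman is the call 24-48 hours after discharge. Both visits that could detect a later clot or wound infection depend on insurance, and nothing is planned in their place for a woman allowed neither. The plan also does not say how women not seen at 6 weeks are counted. If they enter the tables as event-free, a report cannot distinguish no event from no follow-up.

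What is at stake is the completeness of the secondary safety counts. The pilot is meant to lead to a larger multicenter trial, and with so few events expected, one missed clot could turn a count of one into a count of none.

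**Working it through.** **Step 1: is there another route after discharge?** Each candidate was set against the case of a woman whose insurance allows neither visit.

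| Provision | Does it reach her after the call? |
|---|---|
| Reschedule call and letter | No. They follow a no-show, and she has no visit to miss. Their aim is rebooking. |
| Daily adverse-event chart review | No. It is stated for the hospital stay. |
| Resident following the post-operative course | No contact, date or method after discharge is named; the next sentence describes in-hospital checks. |
| Chart review in the Primary outcome paragraph | Possibly. It can be read as covering the endpoints too, but no post-discharge check is scheduled. Confidentiality and Privacy names only the study hospital's charts, so care elsewhere may not appear. |
| 6-week end of follow-up | No. It is an outer limit, is not tied to the complication endpoint, and creates no contact. |

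A woman allowed one visit still has that contact, and the no-show steps apply to her. The gap concerns women allowed neither.

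**Step 2: how large could it be?** The plan gives no figure to reproduce. From Sample Size Calculation, about 40 women are planned, so n = 40/2 = 20 per arm. The remaining inputs are assumptions:

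- k = women per arm allowed neither visit: 2, 4 or 6 of 20 (10-30%)
- s = share of events arising after the call: 0.3 or 0.6
- c = share of those late events caught by study-hospital charts: 0 or 0.5

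Share of all events uncounted = (k/20) × s × (1 − c). For example, (6/20) × 0.6 × 1 = 0.18.

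Upper one-sided 95% bound on the clot risk P, with zero events in 20 TXA women:

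- Full follow-up: 1 − 0.05^(1/20) = 13.9%.
- Otherwise, solve (1 − P)^(20−k) × (1 − P × (1 − s(1 − c)))^k = 0.05.

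| k | s | Uncounted, c = 0 | Bound, c = 0 | Uncounted, c = 0.5 | Bound, c = 0.5 |
|---|---|---|---|---|---|
| 2 | 0.3 | 3% | 14.3% | 1.5% | 14.1% |
| 2 | 0.6 | 6% | 14.8% | 3% | 14.3% |
| 4 | 0.3 | 6% | 14.8% | 3% | 14.3% |
| 4 | 0.6 | 12% | 15.7% | 6% | 14.8% |
| 6 | 0.3 | 9% | 15.3% | 4.5% | 14.6% |
| 6 | 0.6 | 18% | 16.8% | 9% | 15.3% |

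**Step 3: in events.** If the total event risk were 5% (also an assumption), 40 × 0.05 = 2 events would be expected. Between 2 × 0.015 = 0.03 and 2 × 0.18 = 0.36 of them would go uncounted.

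**The case against.** The strongest reply is that the matter is too small to pursue. The number of women affected is unknown and could be zero. Even on the assumptions above, the zero-event bound moves only from 13.9% to at most 16.8%, which says little about thrombosis either way. The primary endpoint is intraoperative, and blinding makes a difference between arms unlikely. This all stands, and it is why the point is a modest improvement and not a threat to the trial's conclusions.

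Other text also softens the gap. The protocol's unblinding and safety committee route applies to a significant event at any time during the study, and each woman receives a copy of the consent form for her primary care doctor. The insurance clause may limit only who is seen in this clinic, so a woman may still receive postpartum care elsewhere. Chart review may well supply the endpoints, which makes the c = 0 columns the worst case. These are fair points, but none schedules a study contact or brings outside care into the study data.

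The remedy has limits too. A call at 6 weeks learns late of an earlier clot, a reported symptom needs a route into routine care, and the consent pages are not available to show whether the call and any records request are covered. These are costs to plan for; they do not remove the reason for the call.

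**Conclusion.** The concern holds. Followed as written, the plan can leave DVT, PE and surgical site infection unascertained after the 24-48 hour call for any woman whose insurance allows neither visit, and it does not say how she would be counted. The text alone establishes this.

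The size is not established. Uncounted events of 3-18% without chart capture, or 1.5-9% with half of late events captured, rest entirely on the assumed k, s and c. The expected harm is some under-counting and slightly weaker safety statements, not bias between arms, although chance imbalance in follow-up is possible with about 20 women per arm. The change should be made because it is cheap.

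**What to change.** Three changes, all to data collection and reporting:

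1. Add one scripted research telephone contact at 6 weeks for every randomized woman without a 6-week clinic visit, whatever her insurance. Ask about clots, infection, readmission and care received elsewhere.
2. Define the complication endpoint as events up to the 6-week limit the protocol already sets.
3. Report by arm the number followed to 6 weeks, and show women not reached separately instead of counting them as event-free.

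Under the assumed 10-30%, this is 40 × 0.10 = 4 to 40 × 0.30 = 12 short calls, plus one to any woman who never rebooks after a no-show (number not given). The investigators already make the 24-48 hour calls, so no new staff are needed. Two or three protocol sentences change. The consent wording should be checked for the call and for outside records, and the protocol should say how a problem disclosed on the call is passed to routine care and to the safety committee. Events reported by telephone are less certain than those found in clinic and may need a records request to confirm.
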